6. GENERAL STATISTICAL CONSIDERATIONS

6.1. General Principles

This is a double-blind, placebo controlled randomized trial with a two-sided type I error rate of 0.05. Secondary hypotheses have been ordered according to relative importance. These will be described according to the appropriate summary statistics, e.g.:

- Percentages/proportions/odds ratios for categorical data. For tabular summaries of percentages/proportions, the denominator (e.g. number of subjects with non-missing data) will be displayed.
- Means, median, and range for continuous data, median for time-to-event data.

Confidence intervals will be generated; for the primary analysis, the confidence level will take into account the group-sequential design of the trial (see Section 6.6 and Section 8.1) whereas 95% confidence intervals will be generated for secondary and exploratory outcomes. Proportions will be estimated using the Kaplan-Meier Day 29 survival estimate with Wald-type confidence intervals assuming large-sample normality with standard errors estimated using Greenwood's formula for variance. For hazard ratio and odds ratio estimates, Wald confidence intervals will also be used. For other efficacy outcomes (e.g. proportions), Wilson or Score confidence intervals will be used. For safety outcomes, exact (e.g. Clopper-Pearson) confidence intervals will be used.

When calculating treatment effects (e.g., differences, hazard ratios, odds ratios) and when using treatment arm as a covariate in regression modeling, the baricitinib + placebo + remdesivir arm will be used as the reference group. For regression modeling that uses strata variables defined in Section 6.4, the first stratum listed for each variable in that section will be used as the reference group.

For the final comparison of Day 29 mechanical ventilation free survival, the following SAS pseudocode will be used to obtain Kaplan-Meier survival estimates, standard errors and confidence intervals, for each treatment within strata. Survival estimates and standard errors will be used to calculate the test statistic and compared to a standard normal distribution as in Section 8.1.1.

```
proc lifetest data=dataset plots=(s) method = km outsurv = survests;
  time TimeVariable * CensorVariable(1);
  strata TreatmentVariable StrataVariable;
run;
```

Note that the interim efficacy analyses will be performed using R. For all interim and final analyses, the software used will calculate the test statistic using the formula in Section 8.1.1.

To perform a stratified Cox proportional hazards model for the final analysis and generate the treatment arm hazard ratio along with its confidence interval, the following pseudocode will be used. For any unstratified analyses, code can be used after the removal of the `strata ... ;` line and strata variable in the `class` statement.

```
proc phreg data=dataset;
  class StrataVariable(ref=StrataLabel) TreatmentVariable(ref=Dxa_RemdesivirLabel);
  model TimeVariable * CensorVariable(1) = TreatmentVariable;
  strata StrataVariable;
  hazardratio TreatmentVariable / diff=ref cl=Wald;
  ods output HazardRatios = HRest;
run;
```

The following SAS pseudocode will be used to perform the proportional odds model with treatment arm and actual baseline ordinal score as covariates and to generate the treatment odds ratio, p-value, and predicted probabilities of the ordinal scale levels by treatment arm and actual baseline ordinal score:

```
proc logistic data=dataset
  plots(only)=effect(x=ResponseVariable sliceby= actualbaselinestrata
    *TreatmentVariable individual connect);
  class actualbaselinestrata(param=ref ref=category5)
    TreatmentVariable(param=ref ref=RemdesivirLabel);
  model ResponseVariable = TreatmentVariable StrataVariable;
  odsratio TreatmentVariable;
  ods output OddsRatiosWald = ORest;
run;
```

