		# of Subj.	# of Dev.	# of Subj.	# of Dev.	# of Subj.	# of Dev.	# of Subj.	# of Dev.	# of Subj.	# of Dev.	# of Subj.	# of Dev.	# of Subj.	# of Dev.	# of Subj.	# of Dev.	# of Subj.	# of Dev.
Treatment administration	Any type	x	x	x	x	x	x	x	x	x	x	x	x	x	x	x	x	x	x
	Required procedure done incorrectly	x	x	x	x	x	x	x	x	x	x	x	x	x	x	x	x	x	x
	Study product temperature excursion	x	x	x	x	x	x	x	x	x	x	x	x	x	x	x	x	x	x
	Other	x	x	x	x	x	x	x	x	x	x	x	x	x	x	x	x	x	x
Blinding policy/procedure	Any type	x	x	x	x	x	x	x	x	x	x	x	x	x	x	x	x	x	x
	Treatment unblinded	x	x	x	x	x	x	x	x	x	x	x	x	x	x	x	x	x	x
	Other	x	x	x	x	x	x	x	x	x	x	x	x	x	x	x	x	x	x

^a[X] additional subjects are included in the 'All Subjects' column that were enrolled with a baseline ordinal score of 4. [Include as applicable]

Table with similar format:

Table 14: Distribution of Major Subject Specific Protocol Deviations by Category, Type, Treatment Group, and Actual Baseline Ordinal Score – mITT Population

Table 15: Mechanical Ventilation-free Survival by Day 29 by Treatment Group and Actual Baseline Ordinal Score

Analysis Population	Treatment Group	Actual Baseline Ordinal Score	Number Subjects requiring Mechanical Ventilation by Day 29	Number Subjects Dying by Day 29	Day 29 Mechanical Ventilation-Free Survival		HR		P-value
					Estimate	95% CI	Estimate	95% CI	
mITT Population	Baricitinib + PBO + RDV (N=X)	5	x	x	x.x	x.x, x.x	x.xx	x.xx, x.xx	--
	PBO + Dexamethasone + RDV (N=X)		x	x	x.x	x.x, x.x			
	Baricitinib + PBO + RDV (N=X)	6	x	x	x.x	x.x, x.x	x.xx	x.xx, x.xx	--
	PBO + Dexamethasone + RDV (N=X)		x	x	x.x	x.x, x.x			
	Baricitinib + PBO + RDV (N=X)	Baseline Clinical Status 5 or 6	x	x	x.x	x.x, x.x	x.xx	x.xx, x.xx	0.xxx
	PBO + Dexamethasone + RDV (N=X)		x	x	x.x	x.x, x.x			
	Baricitinib + PBO + RDV (N=X)	Any Baseline Ordinal Score	x	x	x.x	x.x, x.x	x.xx	x.xx, x.xx	--
	PBO + Dexamethasone + RDV (N=X)		x	x	x.x	x.x, x.x			

Repeat for the As Treated Population and ITT population.

N= Number of subjects in the specified treatment group, actual baseline ordinal score, and analysis population.

n = Number of subjects.

Mechanical Ventilation-Free Survival are Kaplan-Meier Estimates at Day 29 study visit

HR is the ratio of the hazard of mechanical ventilation or death in each treatment group estimated from the Cox model. The ratio is to PBO + Dexamethasone + RDV to Baricitinib + PBO + RDV.

HRs for the 'combined ordinal score groups' are the hazard ratio from the stratified Cox Model.

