				Estimate	95% CI	Estimate	95% CI	Estimate	95% CI	Estimate	95% CI		
mITT Population	Baricitinib + PBO + RDV (N=X)	5	x	x.x	x.x, x.x	x.x	x.x, x.x	x.x	x.x, x.x	x.xx	x.xx, x.xx	--	
	PBO + Dexamethasone + RDV (N=X)		x	x.x	x.x, x.x	x.x	x.x, x.x	x.x	x.x, x.x				
	Baricitinib + PBO + RDV (N=X)	6	x	x.x	x.x, x.x	x.x	x.x, x.x	x.x	x.x, x.x	x.xx	x.xx, x.xx	--	
	PBO + Dexamethasone + RDV (N=X)		x	x.x	x.x, x.x	x.x	x.x, x.x	x.x	x.x, x.x				
	Baricitinib + PBO + RDV (N=X)	Baseline Clinical Status 5 or 6	x	x.x	x.x, x.x	x.x	x.x, x.x	x.x	x.x, x.x	x.xx	x.xx, x.xx	0.xxx	
	PBO + Dexamethasone + RDV (N=X)		x	x.x	x.x, x.x	x.x	x.x, x.x	x.x	x.x, x.x				
	Baricitinib + PBO + RDV (N=X)	Any Baseline Ordinal Score ^a	x	x.x	x.x, x.x	x.x	x.x, x.x	x.x	x.x, x.x	x.xx	x.xx, x.xx	--	
	PBO + Dexamethasone + RDV (N=X)		x	x.x	x.x, x.x	x.x	x.x, x.x	x.x	x.x, x.x				
Repeat for the As Treated Population.													
N = Number of subjects in the specified treatment group, actual baseline ordinal score, and analysis population.													
n = Number of recovered subjects.													
HR is the ratio of the hazard of recovery in each treatment group estimated from the Cox model. The ratio is PBO + Dexamethasone + RDV to Baricitinib + PBO + RDV.													
HRs for the 'Baseline Clinical Status 5 or 6' and 'Any Baseline Clinical Status' groups are the hazard ratios from the stratified Cox Model.													
P-value calculated using the stratified log-rank test													
^a [X] additional subjects are included in the 'Any Baseline Ordinal Score' row that were enrolled with a baseline ordinal score of 4. [Include as applicable]													

Programming Notes:

The p-value for the stratified log-rank test in the (5 or 6) subgroup will only be reported if the p-value for the "Baseline Ordinal Score 5 or 6" analysis is significant (see Section 6.8).

Table 29: Time to Recovery by Day 29 by Treatment Group and Baseline Ordinal Score: Sensitivity and Exploratory Analyses – mITT Population, Actual Baseline Ordinal Score 5 or 6

Model	Treatment Group	Actual Baseline Ordinal Score	HR		Interaction P-value ^a	
			Estimate	95% CI		
Fine-Gray	Baricitinib + PBO + RDV (N=X)	5	x.xx	x.xx, x.xx	--	
	PBO + Dexamethasone + RDV (N=X)					
	Baricitinib + PBO + RDV (N=X)	6	x.xx	x.xx, x.xx		
	PBO + Dexamethasone + RDV (N=X)					
	Baricitinib + PBO + RDV (N=X)	Baseline Ordinal Score 5 or 6	x.xx	x.xx, x.xx		
	PBO + Dexamethasone + RDV (N=X)					

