Day 60	5	X	x.x	x.x, x.x	X	x.x	x.x, x.x
	6	X	x.x	x.x, x.x	X	x.x	x.x, x.x
	Baseline Ordinal Score 5 or 6	X	x.x	x.x, x.x	X	x.x	x.x, x.x
	Any Baseline Ordinal Score ^b	X	x.x	x.x, x.x	X	x.x	x.x, x.x

N = Number of subjects in the specified treatment group and analysis population.

n = Number of subjects in a given treatment group who died by the given timepoint

^a Mortality Rate is the Kaplan-Meier estimate.^b [X] additional subjects are included in the ‘Any Baseline Ordinal Score’ row that were enrolled with a baseline ordinal score of 4. [Include as applicable]

Table with similar format:

Table 69: Deaths by Day 15 or Day 29 by Treatment Group and Actual Baseline Ordinal Score – As Treated Population

Table 70: Time to Death through Day 15 and 29 by Treatment Group and Actual Baseline Ordinal Score – mITT Population

Study Day	Treatment Group	Actual Baseline Ordinal Score	n	HR		P-value	
				Estimate	95% CI		
Day 15	Baricitinib + PBO + RDV (N=X)	5	x	x.xx	x.xx, x.xx	--	
	PBO + Dexamethasone + RDV (N=X)		x				
	Baricitinib + PBO + RDV (N=X)	6	x	x.xx	x.xx, x.xx		
	PBO + Dexamethasone + RDV (N=X)		x				
	Baricitinib + PBO + RDV (N=X)	Baseline Ordinal Score 5 or 6	x	x.xx	x.xx, x.xx	x.XXX	
	PBO + Dexamethasone + RDV (N=X)		x				
	Baricitinib + PBO + RDV (N=X)	Any Baseline Ordinal Score ^a	x	x.xx	x.xx, x.xx		
	PBO + Dexamethasone + RDV (N=X)		x				
Day 29	Baricitinib + PBO + RDV (N=X)	5	x	x.xx	x.xx, x.xx	--	
	PBO + Dexamethasone + RDV (N=X)		x				
	Baricitinib + PBO + RDV (N=X)	6	x	x.xx	x.xx, x.xx		
	PBO + Dexamethasone + RDV (N=X)		x				
	Baricitinib + PBO + RDV (N=X)	Baseline Ordinal Score 5 or 6	x	x.xx	x.xx, x.xx	x.XXX	
	PBO + Dexamethasone + RDV (N=X)		x				
	Baricitinib + PBO + RDV (N=X)	Any Baseline Ordinal Score ^a	x	x.xx	x.xx, x.xx		
	PBO + Dexamethasone + RDV (N=X)		x				

N= Number of subjects in the specified treatment group and analysis population.

n = Number of subjects who died by the specified study day.

HR is the ratio of the hazard of Death in each treatment group estimated from the Cox model. The ratio is Baricitinib + PBO + RDV to PBO + Dexamethasone + RDV.

HR for the 'Baseline Ordinal Score 5 or 6' and 'Any Baseline Ordinal Score' group is the hazard ratio from the stratified Cox Model.

P-value calculated using the stratified Log-rank test.

^a [X] additional subjects are included in the 'Any Baseline Ordinal Score' row that were enrolled with a baseline ordinal score of 4. [Include as applicable]**Programming Notes:**

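### The SAP contradicts itself on the reference arm for hazard and odds ratios, so the hazard ratios in the primary, progression and recovery tables would be labelled as the reciprocal of what the code computes

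*SAP*

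**What the plan says.** The SAP fixes the direction of treatment ratios in three kinds of place.

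- **General rule (Section 6.1).** For differences, hazard ratios, odds ratios and regression models, "the baricitinib + placebo + remdesivir arm will be used as the reference group". Ratios are therefore dexamethasone over baricitinib.
- **Code (Section 6.1).** The Cox block is introduced with the purpose "To perform a stratified Cox proportional hazards model for the final analysis and generate the treatment arm hazard ratio along with its confidence interval". It sets "TreatmentVariable(ref=Dxa_RemdesivirLabel" and requests "hazardratio TreatmentVariable / diff=ref cl=Wald". The proportional-odds block sets "TreatmentVariable(param=ref ref=RemdesivirLabel".
- **Table shells (Appendix 1).** Tables 15 and 23 carry the footnote "The ratio is to PBO + Dexamethasone + RDV to Baricitinib + PBO + RDV". Tables 16, 24, 28 and 29 say "The ratio is PBO + Dexamethasone + RDV to Baricitinib + PBO + RDV". Tables 36, 70 and 77 say "The ratio is Baricitinib + PBO + RDV to PBO + Dexamethasone + RDV". The titles of Tables 21 and 22 give the Day 15 odds ratio as baricitinib relative to dexamethasone.

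Table 15 also states that its hazard ratio for the combined ordinal-score groups comes from the stratified Cox model, which is the model that the Section 6.1 code fits.

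**The concern.** ACTT-4 compares two active regimens, both given with remdesivir. There is no inactive arm from which a reader could infer what a ratio below 1 means, so the label carries the interpretation. If the code and the footnote disagree, the printed ratio and its confidence limits are attached to the wrong drug.

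The tables also disagree among themselves. Death is part of the primary endpoint, yet the primary table runs dexamethasone over baricitinib and the mortality table runs the other way. Recovery (Table 28) and improvement (Table 36) are both favourable events and also run in opposite directions. A programmer cannot satisfy the Section 6.1 sentence, the Section 6.1 code and all the shells at once, and the SAP does not say which prevails.

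**Working it through.** **Step 1: direction by source.**

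| Source in the SAP | Direction |
|---|---|
| Section 6.1 sentence | dexamethasone / baricitinib |
| Section 6.1 Cox code | baricitinib / dexamethasone |
| Section 6.1 proportional-odds code | not determined by the label |
| Tables 15, 16 (primary endpoint) | dexamethasone / baricitinib |
| Tables 23, 24 (progression to 6, 7 or 8) | dexamethasone / baricitinib |
| Tables 28, 29 (recovery) | dexamethasone / baricitinib |
| Tables 21, 22 (Day 15 odds ratio) | baricitinib / dexamethasone |
| Table 36 (improvement) | baricitinib / dexamethasone |
| Table 70 (death) | baricitinib / dexamethasone |
| Table 77 (safety composite) | baricitinib / dexamethasone |

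The Cox code direction follows from two settings: dexamethasone is the reference level, and the hazard-ratio statement compares the other level with the reference. Nothing in the SAP says that the ratio is inverted before printing. The conflict is therefore between the Section 6.1 sentence with six footnotes on one side, and the Cox code with five shells on the other.

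**Step 2: the inputs for an illustration.** The SAP states no hazard ratio. Its design case (Section 5, Table 1, second row) has Day 29 ventilation-free survival of 0.85 on dexamethasone and 0.90 on baricitinib, with 1382 subjects in total. To confirm these inputs, I reproduced the stated power, assuming 1:1 allocation (691 per arm) and two-sided alpha 0.05:

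- Standard error, unpooled = √[(0.85×0.15 + 0.90×0.10)/691] = √(0.2175/691) = 0.01774.
- z = 0.05/0.01774 = 2.818; power = Φ(2.818 − 1.960) = 80.5%. The pooled-variance version gives 80.3%.
- The SAP states 80% (exact score) and 80.5% (Kaplan-Meier with Greenwood). The figures agree.

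**Step 3: the hazard ratio in each direction.** Under proportional hazards, HR = ln S(baricitinib) / ln S(dexamethasone).

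- Direction of the code: ln(0.90)/ln(0.85) = (−0.1054)/(−0.1625) = 0.648.
- Direction of the Table 15 footnote: 1/0.648 = 1.543.
- Simulated Cox fits (100,000 per arm, exponential times, follow-up to 28 days) gave 0.66 with dexamethasone as reference and 1.52 with baricitinib as reference, confirming the directions.
- Over all seven rows of Table 1, the code direction gives 0.480 to 0.740 and the footnote direction requires 1.351 to 2.085.

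A printed 0.65 under the Table 15 footnote would read as a 35% lower hazard of ventilation or death on dexamethasone (1 − 0.65), although baricitinib is the better arm in this scenario.

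**Step 4: what does not change.** The Section 8.1.1 statistic squares the weighted sum of the between-arm differences, so swapping the arms leaves it unchanged. The log-rank p-values are likewise symmetric in the arms. The Kaplan-Meier proportions and the power do not involve a reference arm.

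**Step 5: where a reversal could be seen.** Table 15 prints ventilation and death counts and a Kaplan-Meier proportion for each arm beside the hazard ratio. Table 23 does the same for progression, and Table 28 prints quartiles of time to recovery by arm. The shells of Tables 16, 24 and 29 hold hazard ratios with no arm-level proportion or time.

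**The case against.** The strongest reply is that no inference is affected. The primary analysis is a Kaplan-Meier chi-square test, the Cox models for the primary endpoint are sensitivity analyses in Section 8.2.1, and mortality and recovery are tested by log-rank. This stands in full. A reader might infer that the primary result itself could be reversed; the documents do not support that. The fault concerns hazard ratios that accompany the tests.

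Second, a reversal would be noticed. This holds for Tables 15, 23 and 28, but not for Tables 16, 24 and 29 read alone.

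Third, the code is pseudocode with placeholders. For the proportional-odds block this narrows the point. A reader might infer that the block would fail because no such level exists, but `RemdesivirLabel` is a placeholder, and the fair criticism is only that it does not say which arm is meant, since both receive remdesivir. The titles of Tables 21 and 22 do give a direction, though it is opposite to the Section 6.1 sentence. The Cox block is different: its label clearly names dexamethasone, and the SAP says that the code will be used.

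Fourth, ratios that run in different directions in different tables are not wrong if each is labelled correctly. That is true. It is then a matter of readability, and only the mismatch between code and label is an error.

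Finally, the restricted mean differences in Tables 34 and 75 name the arms in opposite order, and a reader might infer opposite signs. The wording, a difference between two arms, does not say which is subtracted from which. The direction is unstated rather than shown to conflict.

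**Conclusion.** The contradiction is real, and nothing in the SAP resolves it. Run as written, the plan would label the hazard ratios of the primary, progression and recovery tables as the reciprocal of what was computed, and the Day 15 odds ratio has one direction in Section 6.1 and the other in its table titles.

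At the design case the discrepancy is 0.65 against 1.54. That figure is illustrative: it assumes proportional hazards, the planned proportions, and code output printed without inversion under an unchanged footnote.

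The damage is confined to the labelling of accompanying estimates. The point still merits correction before tables are produced, because in a head-to-head trial the label alone says which drug a ratio favours.

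**What to change.** Choose one reference arm and apply it to the Section 6.1 sentence, both code blocks and every hazard-ratio or odds-ratio footnote or title.

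- **Dexamethasone as reference** is a natural choice: it matches the Cox code and Tables 21, 22, 36, 70 and 77. The Section 6.1 sentence, the proportional-odds reference label and the footnotes of Tables 15, 16, 23, 24, 28 and 29 would change.
- **Baricitinib as reference** is equally acceptable if used throughout. The reference labels in both code blocks, the titles of Tables 21 and 22 and the footnotes of Tables 36, 70 and 77 would change.

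In either case, add to each footnote which side of 1 favours which arm, because the favourable side differs between harmful events (ventilation, death) and beneficial ones (recovery, improvement). State the order of subtraction for the restricted mean differences in Tables 34 and 75. Tables built on these shells should take the corrected footnote.

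The cost is wording and code-label edits. No new analysis, data or sample-size work is needed.

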6.2. Timing of Analyses

6.2.1. Interim Analyses

A DSMB will monitor ongoing results to ensure patient well-being and safety as well as study integrity. The DSMB will be asked to recommend early termination or modification only when there is clear and substantial evidence of a treatment difference. More details about the interim analyses are described in Section 6.6.1 and Section 6.6.3 below. The summaries to be generated for the interim analysis are provided in the separate DSMB shell report.

The separate Futility Analysis Plan describes the methods for the Futility Analysis conducted in April 2021.

6.2.2. Final Analyses

The final analyses of all outcomes and planned summaries/listings will be performed on the final full locked database through Day 29 and provided in the final report. If substantial Day 60 data is available, results from Day 60 may also be included in the final report and this SAP amended appropriately. In addition, the final report may be amended to include the totality of the Day 60 data when locked.

6.3. Analysis Populations

Summaries and analysis of safety data will be presented for the As Treated Population. Summaries and analysis of efficacy data will be presented for the modified intention-to-treat (mITT) population and As Treated population.

6.3.1. Intention-to-Treat (ITT) Population

The intention-to-treat (ITT) population includes all subjects who were randomized. ITT subjects will be classified by their randomized treatment assignment and randomized disease severity stratum (i.e., the stratum to which the subject randomized at enrollment, which is not necessarily equivalent to their baseline ordinal score if the subject was mis-stratified).

6.3.2. Modified Intention-to-Treat (mITT) and As Treated Populations

The modified intention-to-treat (mITT) population includes all subjects who were randomized. mITT subjects will be classified by their randomized treatment assignment and actual baseline ordinal score ordinal stratum (i.e., the stratum corresponding to their baseline ordinal score, not necessarily the stratum within which the subject was randomized at enrollment).

The As Treated population includes all randomized subjects who received the study product, even if only one dose was administered.

For As Treated analyses of efficacy outcomes, subjects will be classified by their actual treatment assignment and their actual baseline ordinal score, unless otherwise specified in the table or figure shell. Note that if no subjects are administered the incorrect treatment and all subjects receive at least one dose of baricitinib/placebo, dexamethasone/placebo, the As Treated efficacy analysis will not be performed as they will be identical to the mITT analyses.

For As Treated analyses of safety outcomes, concomitant medications, and medical history, subjects will be classified by their actual treatment assignment and actual baseline ordinal score stratum.

6.4. Covariates and Subgroups

As additional secondary analysis, the primary efficacy outcome will be summarized within each of the baseline actual ordinal score subgroups (5 and 6). Analysis of all secondary outcomes will be performed in subgroups based on the baseline actual ordinal score.

Further subgroup analyses for the primary and key secondary efficacy outcomes will evaluate the treatment effect within the following subgroups:

- Prior Corticosteroid use
 - Yes / No
 - Dexamethasone on the day of randomization / not
 - Number of on-study dexamethasone/placebo infusion (9 vs 10). Some subjects who received dexamethasone on the day of randomization may skip their first post-randomization, on-study dexamethasone / placebo infusion and therefore receive only 9, rather than the expected 10, on-study infusions.
- Geographic region
 - US sites; Non-US sites
 - North American sites; Asian sites; European sites
- Duration of symptoms prior to randomization
 - Quartiles
 - <= 10 days; > 10 days
 - <= Median; > Median
- Race (White; Black/African American; Asian; Other)
- Comorbidities
 - None; Any
 - None, One, Two or more
 - Obese; Non-Obese
- Age (<40; 40-64; 65 and older)
- Sex (Female; Male)

- Randomized strata
 - 5 or 6 (separately) on ordinal scale used for randomization

Note: separate analyses for randomized/actual severity will only be performed if at least one subject is erroneously randomized into the incorrect baseline ordinal score stratum.

Additionally, analyses of all remaining secondary efficacy outcomes and the time to death by Day 15/29 outcomes will evaluate the treatment effect within the following subgroups (among subjects enrolled with baseline ordinal score of 5 or 6 only):

- Duration of symptoms prior to randomization (<= Median; > Median)
- Severity of disease
 - Randomization stratification: 5 or 6 (separately) on ordinal scale.
 - Actual ordinal score at baseline: 5 or 6 (separately) on ordinal scale.

Note: separate analyses for randomized/actual severity will only be performed if at least one subject is erroneously randomized into the incorrect baseline ordinal score stratum.

There will also be a sensitivity analysis of the primary, secondary, and mortality outcomes to evaluate the effect of concomitant therapy including experimental treatment and off-label use of marketed medications that are intended as treatment for COVID-19 and are given to patient prior to and during the study. A blinded review of the concomitant medication data will be performed by the medical monitor to identify medications that fall into any of the following categories of “Medications of Interest”:

- Vaccine for SARS-CoV-2 (Pfizer, Moderna, or other) including 1 or 2 doses received
- Antivirals
 - Protease inhibitors
 - Polymerase inhibitors
- Other Potential Treatments for COVID-19
 - Aplidin® (plitidepsin)
 - Colchicine (Colcrys)
 - Monoclonal antibodies targeting the spike protein of SARS-CoV-2 including casirivimab, imdevimab and bamlanivimab
 - Ivermectin (stromectol, Soolantra, Sklice)
- Corticosteroids
- Renin-angiotensin system (RAS) Inhibitors and HMG-CoA reductase inhibitors (statins)
- Other anti-inflammatory drugs
 - Monoclonal Antibodies Targeting Cytokines
 - Other Biologic Therapies

Summaries of subjects who report use of the categories and subcategories of therapies/treatments will be provided. Note that after the blinded review of the medications, additional categories/sub-categories may be defined and/or categories/sub-categories may be combined.

In addition, the sensitivity analyses will consider the following categories (individually):

- Any Medication of Interest
- Vaccines to SARS-CoV-2
- Antivirals
- COVID-19 treatments
- Monoclonal antibody treatments for COVID-19
- Corticosteroids
- RAS Inhibitors and HMG-CoA reductase inhibitors (statins)
- Other Anti-Inflammatory Drugs

Three initiation and duration groups will be constructed for each of the above categories:

1. Prior and During: Subjects taking medication of interest before randomization and during study (on or after Day 1).
2. Prior Only: Subjects taking medications of interest prior to randomization but stopping prior to randomization.
3. During Only: Subjects initiating medications of interest during the study (on or after Day 1).

For the analysis of mechanical ventilation free survival, subjects will be censored at the time of medication/therapy initiation. For the analysis of the key secondary outcome, if a subject reports use of any of the medications/therapies prior to their Day 15 assessment, then the subject's last clinical status score prior to medication/therapy use will be used as their Day 15 outcome. For the mortality analyses, subjects will be censored at the time of medication/therapy initiation. For the analysis of the proportion of subjects that do not progress to Clinical Status Ordinal Score of 6, 7, or 8 by Day 29, subjects will be censored at the time of medication / therapy initiation. For the recovery analyses, subjects will be censored at the time of medication/therapy initiation. If a subject recovered prior to use of any of the medications/therapies, then the subject will still be counted as a recovery in the sensitivity analysis.

The effect of on-study treatment on select efficacy outcomes will also be explored among subjects who reported use of HMG-CoA reductase inhibitors (statins), angiotensin receptor blockers (ARBs), or angiotensin converting enzyme inhibitors (ACEIs) via subgroup analyses.

Lastly, the effect of treatment on the primary and key secondary efficacy outcomes will be explored via regression modeling controlling for age, duration of symptoms prior to randomization, baseline d-dimer, and baseline CRP values as continuous covariates.

